**Risks:** The DXA (for measures of body composition) involves exposure to ionizing radiation. The DXA scans (total body,) at 2 times during the study involve a total effective radiation exposure of about 60 mrem. DXA involves  $< 3\%$  of the annual maximum non-therapeutic radiation exposure to the whole body recommended by the FDA (5000 mrem/year). Urine pregnancy will not be performed prior to DXA scans, as all women will be post- childbearing state (ie, post-menopausal).

**Plans to minimize risk:** The risk of radiation exposure is minimized by having trained technicians administer the DXA, thereby reducing the likelihood of needing repeat assessments.

Justification: DXA is a routine test obtained in clinical practice and will provide important data regarding the impact of exercise on lean and fat mass.

**Physical function tests and Physical Activity Assessments:** The **primary physical function outcome will be 400-MWT**, a well-established measure shown to better discriminate early physical function decline among higher functioning adults, and is a reliable outcome in clinical trials, including the LIFE Trial. The Short Performance Physical Battery (SPPB) and a modified version (mSPPB) will be obtained. The SPPB is an objective assessment of physical function associated with short-term mortality, disability, and hospitalizations. The mSPPB improves discrimination of physical function by increasing repeat chair stands from 5 to 10, standing balance test for 30 seconds instead of 10, and adding a single leg stand. Physical function will be measured every 4 weeks by a research assistant blinded to intervention arm. The 400-MWT, SPPB, and mSPPB will be administered at both sites using standard scripts. PA will be measured using the ActiGraph accelerometer (ActiGraph, LLC, Fort Walton Beach, FL). Participants will wear the monitor for 7-10 consecutive days on their nondominant hip. A valid wear cycle will have data recorded for  $\geq 10$  hours/day for  $\geq 4$  days. Non-wear time will be defined as 0 counts/minute for  $\geq 60$  minutes. We will require consecutive epochs outside of the activity threshold for wear-time to resume. Participants not meeting standards will be asked to re-wear the ActiGraph. Data will be sampled at 30 Hz, using 60-second epochs, and the normal filter. We have found that when given the second opportunity, 95% of participants met standards. Activity  $\geq 2690$  counts/minute and  $\geq 10$  minutes will be defined as exercise.

Risk: The risks associated with the physical function tests are minimal and include a) slight muscular soreness or strain; b) a small possibility of loss of balance or fall, and c) a very small possibility of angina from overexertion.

Plans to minimize risk: Physical function assessments are meant to mimic a patient's daily activities, such as walking across the room, rising from a chair, and balancing to reach for an overhead object. These assessments pose little risk beyond what would be encountered in a day's activities. To minimize the risks of physical function testing, an experienced examiner will administer the tests and instruct participants to stop if they are uncomfortable or fearful at any time during the test. Participants will be allowed ample rest time between tests.

Justification: Physical function measures are predictive of subsequent disability, hospitalizations, falls, and mortality and are safely administered in multiple large cohorts of aging individuals.

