#### Exclusion criteria:

- **Weight over 450 pounds** (due to limitations of the DXA machine)
- **Use of sex hormone therapy**, if on for  $\leq 3$  months (stable doses for  $>3$  months will be permitted)
- **Use of other hormone replacement**, if on for  $\leq 3$  months (stable doses  $>3$  months will be permitted)
- **Anemia** (Hemoglobin  $\leq 9$  g/dL for women or  $\leq 10$  g/dL for men) due to contribution to fatigue,
- Diagnosis of **mitochondrial disease**,
- For participants undergoing the muscle biopsy only, use of anticoagulant therapy other than low dose aspirin that cannot be held for at least 7 days for the muscle biopsy. Aspirin and non-steroidal use will be permitted but will be held for 7 days prior to the muscle biopsy, and can be resumed following the biopsy.
- For the MRI/MRS optional imaging: participants with implanted devices (i.e. pacemaker or insulin pumps), have severe claustrophobia, and females who are pregnant will be excluded.
- Due to the expected fatigue associated with COVID-19 and potential infection risk, anyone with a diagnosis of COVID will not be eligible for enrollment until at least 30 days after symptom resolution and return to baseline level of function.
- **Active substance abuse** or other factors that could prevent compliance or safety with study visits, at the discretion of the site investigator,
- Reasons for **medical exclusion**, as determined by [name] or a provider at the University of Washington:
  - **Uncontrolled hypertension** defined as resting systolic blood pressure  $>150$  mmHg or diastolic blood pressure  $>90$  mmHg; participants who do not meet these criteria at first screening will be re-evaluated, including follow-up evaluation by their primary care provider with initiation or adjustment of anti-hypertensive medications,
  - **Unstable ischemic heart disease** (e.g., angina, ST segment depression) or **serious arrhythmias** at rest or during the graded exercise test without negative follow-up evaluation will be cause for exclusion; follow-up evaluation must include diagnostic testing (e.g., thallium stress test) with interpretation by a cardiologist,
  - **New York Heart Association Class III or IV congestive heart failure**, clinically significant aortic stenosis, uncontrolled angina, or uncontrolled arrhythmia,
  - **Pulmonary disease** requiring the use of supplemental oxygen at rest or with physical exertion,

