*Baseline visit #2* will include a fasting blood draw (i.e., complete blood count, metabolic panel, HIV-1 RNA, CD4 count, PBMCs, FSH, and stored sample for future analyses) and vastus lateralis muscle biopsy (this will be optional), both collected between 8-10am. CD4 count does not to be measured if results from clinical care are available within the prior 12 months HIV-1 RNA if available within the prior 3 months and no reason to expect failure of treatment (i.e, stopped ART).. Complete blood count, complete metabolic panel, and thyroid stimulating hormone does not to be measured if results from clinical care is also available within the prior 3 months. The blood draw and the muscle biopsy will be repeated following the 16-week intervention. Blood labs may need to be repeated or redrawn at subsequent screening visits. Specimens of the *vastus lateralis* muscle will be obtained by percutaneous biopsy from fasted participants who have refrained from exercise for  $\geq 48$  hours. After cleansing the thigh with chlorhexidine, 1% lidocaine without epinephrine will be injected subcutaneously. A 3-5 mm incision will be made in the skin and fascia over the belly of the *vastus lateralis*, and 100-150 mg of muscle tissue will be removed using a Bergstrom side-cutting biopsy needle. The incision will be closed using Steri-strips; a compression wrap and ice will be applied for 30 minutes. Participants will be instructed on wound care and will be contacted by study staff 48-72 hours post-procedure to ensure healing. [name] has performed over 80 biopsies and [name] has performed over 50 biopsies with no prior complications and excellent tissue yield (. Following the biopsy, study staff will explain the *Lee Fatigue Scale* (LFS) and use of the accelerometer (see below) to the participant.

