#### D. Description, Risks and Justification of Procedures and Data Collection Tools:

**Muscle biopsy.** Participants agreeing to muscle biopsy will have a biopsy prior to and at the completion of the 16 week intervention. Participants will be advised to refrain from any physical activity for at least 48 hours following the biopsy. Non-steroidal anti-inflammatories or aspirin are held for 7 days prior to the biopsy. If participants are taking direct oral

anticoagulants, this will be held for 48 hours prior to the procedure (72 hours if creatinine clearance is 30-50 and taking dabigatran) if approved by their primary provider. Therapy can be resumed 24 hours after the procedure, or as instructed by their physician. At study completion, subjects will be asked to return within 10 days of the final exercise session for a muscle biopsy. The exercise intervention will begin >48 hours after the initial biopsy, but within 28 days. Participants will be asked to abstain from alcohol or caffeinated beverages after 1300h and to fast from any food or drink beginning at 9pm with the exception of water. The biopsy will be completed prior to 10am local time. Percutaneous samples of the vastus lateralis muscle will be obtained. After cleansing the area of the thigh with antiseptic (e.g., chlorhexidine, Betadine solution), 1% lidocaine (without epinephrine) will be injected under the skin. A 3-5 mm incision will be made in the skin and fascia over the belly of the vastus lateralis, and 100-150 mg of muscle tissue will be removed using a Bergstrom side-cutting biopsy needle with suction applied. The incision will be closed and a compression wrap and ice will be applied to the incision area for 30-45 minutes. The patient will be given instructions for wound care before discharge.

**Risks:** The risks associated with muscle biopsy include brief, mild burning pain from the local anesthetic (lidocaine), more than mild discomfort during the acquisition of tissue (about 10% of cases), and infection (less than 0.4% of cases). Allergy to the anesthetic (skin swelling or rash) occurs rarely. There may be persistent numbness in the biopsy area.

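### For direct oral anticoagulants before the optional muscle biopsy, the exclusion criteria and the procedure text give different hold periods, which must be reconciled

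*Combined protocol and SAP*

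**What the plan says.** Two sections of the protocol deal with stopping anticoagulants before the biopsy.

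- **Section IV.B, Exclusion criteria.** For biopsy participants only, the criterion is "use of anticoagulant therapy other than low dose aspirin that cannot be held for at least 7 days for the muscle biopsy". It covers all anticoagulants except low-dose aspirin and has no separate rule for direct oral agents. On aspirin and non-steroidals it continues: "Aspirin and non-steroidal use will be permitted but will be held for 7 days prior to the muscle biopsy".
- **Section IV.D, Muscle biopsy.** For participants on direct oral agents the text reads "this will be held for 48 hours prior to the procedure", with 72 hours for dabigatran at creatinine clearance 30-50, and it then requires the primary provider's approval. On restarting: "Therapy can be resumed 24 hours after the procedure, or as instructed by their physician". On aspirin and non-steroidals: "Non-steroidal anti-inflammatories or aspirin are held for 7 days prior to the biopsy". No interval is given for anticoagulants other than direct oral ones.

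The plan to minimize biopsy risk in section IV.D refers back to the biopsy-specific criteria: a trained clinician is to perform the procedure on people who meet them.

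The scope is limited. The description of baseline visit 2 (section IV.C) lists "vastus lateralis muscle biopsy (this will be optional"), and the table of study measures by site marks the biopsy for UW/UCD and not for UAB. Those who agree have it twice: "Participants agreeing to muscle biopsy will have a biopsy prior to and at the completion of the 16 week intervention".

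**The concern.** Both sections govern the same drugs before the same invasive procedure, and their periods differ by several days. The biopsy is done for research and is optional, so the instruction on interrupting a prescribed treatment should be unambiguous. The protocol itself treats the hold as a safety matter: it asks for provider approval, adjusts one interval for renal function, and rests its risk plan on the biopsy criteria.

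Two things are left open. One is whether a participant approved for the shorter hold, but not for 7 days, may be biopsied at all. The other is which hold applies, at baseline and again at week 16, to a participant who is eligible. Two sites perform the biopsy and could answer differently.

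**Working it through.** The plan has no figure to reproduce. The check sets the two texts side by side and converts units.

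**Inputs.** Eligibility text (IV.B): at least 7 days. Procedure text (IV.D): 48 h, or 72 h for dabigatran with creatinine clearance 30-50; restart from 24 h after the procedure or as the physician instructs. Biopsies per consenting participant: 2.

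**Arithmetic.**
- 7 days × 24 = 168 h.
- Shortfall: 168 − 48 = 120 h; 168 − 72 = 96 h.
- Share of the eligibility period: 48/168 = 29%; 72/168 = 43%.
- Counting the 24 h before restart as part of the hold: 48 + 24 = 72 h and 72 + 24 = 96 h, that is 3 to 4 days, still under 7.
- Pre-procedure hold over both biopsies: at least 2 × 7 = 14 days under IV.B, against 2 × 2 = 4 or 2 × 3 = 6 days under IV.D.

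**Cases.**

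| Participant | Exclusion criteria (IV.B) | Procedure text (IV.D) |
|---|---|---|
| Direct oral anticoagulant; 7-day hold possible and the shorter hold approved | Eligible | Held 48 or 72 h; no mention of 7 days |
| Direct oral anticoagulant; 48 or 72 h approved, 7 days not possible | Excluded from biopsy | Stated condition met |
| Direct oral anticoagulant; no hold possible or approved | Excluded from biopsy | Condition not met |
| Other anticoagulant | 7-day test applies | No interval given |

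The third row agrees and the fourth contains no contradiction. The second row conflicts on eligibility. The first leaves the actual hold unclear.

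**Cross-checks.** The aspirin and non-steroidal hold is 7 days in both sections, so the mismatch is specific to direct oral anticoagulants. Both texts are current protocol wording, and no other section explains the difference.

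**The case against.** The strongest defence is that the two texts do different jobs. The exclusion criterion, read literally, tests whether the drug could be stopped for 7 days, while the procedure text says how long it is actually stopped. Staff could screen on the first, hold for the second, and satisfy both. The drafting lends some support: for aspirin and non-steroidals the criterion states an actual hold, but for anticoagulants it states only an ability. The risk plan's reference to the biopsy criteria also suggests that the criterion applies first, so the participant in the second row of the table would not be biopsied.

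Much of this stands. A reader might infer that staff cannot possibly comply with both sections; the documents do not support that. The defence does not, however, remove the need to clarify. On the literal reading the protocol screens on an interval that the procedure never uses, and gives no reason. The procedure text makes its own condition provider approval and does not mention a 7-day test. The neighbouring sentence on aspirin and non-steroidals uses 7 days as a real hold, so many readers would take the anticoagulant figure the same way.

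A reader might also infer a threat to Aim 2, because muscle state 3 respiration depends on who is biopsied. That is weak. The baseline biopsy is at visit 2 and randomization at the end of visit 3, so entry to the biopsy is decided before allocation, and randomization is balanced by site. Neither text distinguishes the arms at week 16. The respiration measure in blood cells is not touched by the rule.

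Finally, the list of biopsy risks in section IV.D names neither bleeding nor thrombosis, so the documents cannot size any harm. The hour counts above measure the disagreement between the texts, not a risk.

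**Conclusion.** The inconsistency is real but narrow. For direct oral anticoagulant users who opt into the biopsy at the Washington and Colorado sites, the eligibility criterion works from at least 168 hours and the procedure text from 48 or 72 hours, and the protocol does not say how the two fit together. It is therefore unclear whether someone approved only for the shorter hold may be biopsied, and which hold applies at each of the two biopsies.

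The documents do not give the number of people affected, and it may be small. The case rests on participant safety and on sites working to the same rule, not on the statistics: no change to sample size or power follows, and no bias in the HIIT versus CME comparison is shown. The conclusion assumes that no manual of procedures outside these documents already settles the matter. It takes no position on which period is right.

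**What to change.** The clinical investigators should reconcile the exclusion criterion in section IV.B with the muscle biopsy text in section IV.D, so that one consistent rule appears in both. If a screening test and a different operating hold are both intended, the protocol should say so and state which decides eligibility. The reference to the biopsy-specific criteria in the risk plan should then point clearly to that rule. The biopsy sites should be asked which rule they have applied so far, at baseline and at week 16. No interval is proposed here.

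The cost is one protocol clarification and a site memo. No analysis or sample size text needs to change.

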*Screening/Baseline Assessments.* After obtaining informed consent, the first of three baseline visits will include medical history, physical exam, and graded exercise test (GXT) with peak aerobic power ( $VO_{2peak}$ ). GXT (baseline): We will screen out volunteers with evidence of ischemic heart disease, serious arrhythmias, or abnormal heart rate/blood pressure responses to exercise. The test will begin at a comfortable walking speed and 0% elevation; speed will be maintained and the grade increased by 2% every 2 min, until the participant reaches volitional exhaustion or the test is otherwise terminated. Electrocardiogram will be monitored throughout. Procedures for minimizing risks during exercise testing are described below.  $VO_{2peak}$  will be used to prepare the prescriptions for aerobic exercise and to determine the effects of training ( $\Delta$  baseline to week 16). The  $O_2$  and  $CO_2$  content of expired air will be measured continuously by open circuit spirometry and averaged every 30 sec using an automated online system. In the absence of evidence that  $VO_{2max}$  has been attained ( $\geq 2$  of: a plateau in  $VO_2$ , respiratory exchange ratio  $\geq 1.10$ , maximal heart rate within 10 beats of age-predicted), the maximum measured  $VO_2$  will be deemed  $VO_{2peak}$ . Increases in  $VO_{2peak}$  in response to training will verify that the exercise was of sufficient intensity.

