**Plan to Minimize Risk:** Risks of the muscle biopsy procedure will be minimized by having a trained clinician perform the procedure on participants who meet the biopsy-specific criteria listed above. [name] has previously performed more than 80 biopsies and [name] has completed more than 50 biopsies. Participants will be observed following the procedure for any adverse events and given strict instructions for wound care. A phone call will be made within 48-72 h of the biopsy procedure to assess wound healing with a study clinician. Additionally, the study will have a safety officer. Drs. [name] and [name] will review biopsy and exercise safety with the DSMB every 6 months.

**Justification:** Skeletal muscle mitochondria are reflective of insults that may have occurred decades earlier, whereas mitochondrial studies obtained through peripheral blood would only reflect changes over a much shorter time period. Thus the muscle specimens provide a window into mechanisms well beyond what can be collected less invasively and reflect changes in the tissue targeted with the intervention.

**Exercise testing and training:** All participants will engage in a 16-week randomized, supervised exercise intervention (high-intensity interval training [HIIT] vs continuous moderate exercise [CME], followed by a 12-week exercise maintenance intervention in which participants are also randomized to a coaching vs control intervention. The exercise prescription will be based on baseline measure of VO2 maximum (or peak) and 1-RM measurements.

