**Maximal aerobic power (VO2 max).** The measurement of VO2max (or peak) will be used to formulate the prescription for CEx at the screening visit. Increases in VO2max in response to exercise training will also verify that the exercise was of sufficient intensity to induce cardiorespiratory adaptations. During an initial 5-min warm-up, walking speed will be adjusted to elicit a HR that is ~70% of maximal HR (from the screening GXT). Speed will then be held constant and the grade of the treadmill will be increased by 2% every 2 minutes until volitional exhaustion or until the test is stopped (see section 4.1.2b). The O2 and CO2 content of expired air will be measured continuously by open circuit spirometry and averaged every 30 sec using an automated online system (TrueMax 2400; ParvoMedics, Sandy, UT). Objective evidence that VO2max has been attained will include at least 2 of the following: a plateau in VO2 despite an increased energy demand, a respiratory exchange ratio in excess of 1.10, and a maximal HR within 10 beats of the age-predicted value. In the absence of these benchmarks, the maximum measured VO2 will be deemed VO2 peak.

**Muscle strength (1-RM).** Muscle strength will be evaluated as the 1-RM (the maximal weight that can be lifted only 1 time using correct lifting form through the full range of motion) for the upper and lower body REx performed during weeks 1-16. 1RMs will be measured at week 0 and every 4 weeks to week 20. The change in muscle strength from week 0 to 16 will be a secondary outcome measure.

**Exercise Intervention.** Participants will be assigned with equal probability to one of the two exercise intervention arms (high intensity interval training [HIIT] or continuous moderate intensity exercise [CME]) following completion of screening procedures. Randomization procedures will be site-specific, and use permuted blocks with stratification by sex and 10-year age categories (i.e., 50-59 years, 60-69 years, 70-80 years), to assure similar distribution in each arm. The allocation to study arm will remain blinded (masked) to the research assistant conducting the physical function assessments and to laboratory personnel.

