- **Endpoints for exercise tests:** In asymptomatic individuals who do not develop cardiovascular abnormalities, the endpoint for the maximal exercise tests will be achieving 85% of age-predicted maximal heart rate, fatigue that forces cessation of exercise, or increasingly unstable gait. The criteria that will be used to stop the exercise test before meeting the above criteria include the development of: (a) ST-segment depression of more than 0.2 mV that is either horizontal, downsloping, or slowly upsloping (less than 1 mV/sec) and lasts for 0.08 sec, or ST-segment elevation greater than 0.1 mV; (b) chest pain or discomfort; (c) serious arrhythmias, including multifocal PVCs, ventricular tachycardia, or sustained atrial tachyarrhythmias; (d) development of A-V block or other conduction defects; (e) a fall of systolic blood pressure of 10 mmHg or greater from the peak level with increasing exercise intensity; (f) diastolic blood pressure above 110 mmHg or systolic above 220 mmHg; (g) dizziness; (h) ataxic gait; and (i) pallor or cyanosis. If a subject is noted to have osteoporosis (T-score <-2.5, upon screening, he or she will be referred to their primary care physician to discuss the potential risks and benefits of exercise and the need for immediate or delayed treatment for osteoporosis prior to initiating the study. The risks associated with the muscular strength tests are musculoskeletal pain, fatigue, dizziness, and syncope. These risks will be minimized by providing one-on-one instruction in proper exercise

| Table 4. Example Aerobic Exercise Prescriptions                            |     |             |      |            |
|--|-----|-------------|------|------------|
| Participant weight = 78 kg and $\text{VO}_{2\text{peak}}$ = 25.2 ml/kg/min |     |             |      |            |
|  | HRR | # Intervals | kcal | Total time |
| CME   | 60  | 1 x 50 min  | 290  | 50 min     |
| HIITa (low)  | 50  | 4 x 3 min   | 288  | 42 min     |
| HIIT (high)   | 90  | 5 x 4 min   |      |            |
| a alternating low/high-intensity, starting with low-intensity   |     |             |      |            |

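### The stopping rule at 85% of predicted maximal heart rate conflicts with running the VO2peak test to exhaustion, and the plan does not say which maximum defines heart rate reserve

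*Combined protocol and SAP*

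**What the plan says.** Section IV.D, Endpoints for exercise tests, covers asymptomatic people who develop no cardiovascular abnormality. For them, "the endpoint for the maximal exercise tests will be achieving 85% of age-predicted maximal heart rate, fatigue that forces cessation of exercise", or an increasingly unstable gait. The clinical safety stops, (a) to (i), form a separate list of reasons to end a test before those endpoints are reached. The 85% figure is therefore a planned endpoint for well participants and not a safety stop.

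Two other places describe the test that yields VO2peak:

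- Section IV.C, Screening/Baseline Assessments, raises the treadmill grade "until the participant reaches volitional exhaustion or the test is otherwise terminated". This is the same test that screens people out: "GXT (baseline): We will screen out volunteers with evidence of ischemic heart disease".
- Section IV.D, Maximal aerobic power, continues "until volitional exhaustion or until the test is stopped". One of its three signs of a true maximum, of which two are needed, is "a maximal HR within 10 beats of the age-predicted value". The others are a VO2 plateau and a respiratory exchange ratio criterion. "In the absence of these benchmarks, the maximum measured" VO2 is taken as VO2peak.

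On use, section IV.D (Exercise testing and training) states: "The exercise prescription will be based on baseline measure of" VO2 maximum or peak, together with 1-RM. Section IV.C also uses VO2peak to judge the effect of training and to verify that its intensity was sufficient. Change in VO2 maximum to week 16 is exploratory outcome 2 in section IV.A.

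Training targets are 90% and 50% HRR for HIIT and 60% HRR for CME. Section IV.C spells HRR out as heart rate reserve but does not say which maximal heart rate enters it. A maximum is tied to a test only for a warm-up: "walking speed will be adjusted to elicit a HR that is ~70% of maximal HR (from the screening GXT".

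**The concern.** Staff at three sites could follow the text faithfully and end the same test at different points. Where the 85% endpoint is applied to someone who could have gone further, the recorded VO2peak is a truncated value. The fallback rule labels that value as VO2peak but does not correct it.

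Two things are at stake. First, the week 0-16 change can be distorted even if the 85% rule is applied at both visits. Someone who stops from fatigue at baseline, gets fitter, and reaches 85% at week 16 has only the second value capped, so the gain is understated. Second, if heart rate reserve is computed from the peak seen in a capped test, the starting HIIT and CME targets are set too low.

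**Working it through.** The plan states no figure for this point, so the check compares the rules and then sizes the consequence.

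**Inputs from the protocol.** The 85% endpoint and the 10-beat criterion (IV.D); ages 50-80 (Aim 1 and the randomisation strata); 90% and 60% HRR (IV.C); Table 4's example of 78 kg and VO2peak 25.2 ml/kg/min; 5 kcal per litre of oxygen (IV.C).

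**Assumptions not in the protocol.** Predicted maximum M = 220 - age, so 170 to 140 bpm; resting rate R = 55-85 bpm; resting VO2 3.5 ml/kg/min where needed.

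**1. Can a test stopped at 85% meet the 10-beat criterion?** The shortfall is 0.15 x M. It is 10 beats or fewer only if M is at most 10/0.15 = 66.7 bpm. At M = 170 the stop is 144.5 and the shortfall 25.5; at M = 140 they are 119 and 21. The criterion is missed by 11 to 15.5 bpm. With 208 - 0.7 x age instead, the shortfall is 22.8 to 26.0. The criterion cannot be met under either formula.

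**2. How far is VO2peak understated?** This depends on the true maximum.

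- Near-zero case: predicted 160, rest 70, stop 136, true maximum 137.6. The stop is at (136 - 70)/(137.6 - 70) = 66/67.6 = 0.976 of true reserve, so about 2% short.
- Illustration with true maximum equal to predicted: the fraction of reserve at the stop is f = (0.85M - R)/(M - R). It runs from (119 - 85)/(140 - 85) = 0.618 to (144.5 - 55)/(170 - 55) = 0.778.

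To turn f into VO2, first see how Table 4 treats % HRR. Reading it as % VO2peak, CME gives 0.6 x 25.2 x 78/1000 x 5 x 50 = 294.8 kcal (printed 290). HIIT gives (0.9 x 20 + 0.5 x 22) x 25.2 x 78/1000 x 5 = 285.0 kcal (printed 288), taking the 10 minutes outside the intervals at 50%. The table is consistent with that reading.

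- As % VO2peak: 25.2 x f = 15.6 to 19.6, which is 38% to 22% low.
- As % VO2 reserve: 3.5 + 21.7 x f = 16.9 to 20.4, which is 33% to 19% low.

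**3. What does the choice of maximum do to the targets?** Target = R + p x (maximum - R). Replacing M by 0.85M lowers it by p x 0.15M, whatever R is. For p = 0.9 the drop is 18.9 to 23.0 bpm; for p = 0.6 it is 12.6 to 15.3 bpm. Example at age 60 and rest 70: the 90% target is 70 + 0.9 x 90 = 151 with the predicted maximum and 70 + 0.9 x 66 = 129.4 with the capped peak. The 60% target is 124 against 109.6.

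As a share of predicted maximum, the capped 90% target is 0.765 + 0.1R/M = 0.797 to 0.826.

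**4. Is the cap consistent with the training itself?** With the predicted maximum, 90% HRR equals 0.9M + 0.1R, which exceeds 0.85M for every resting rate. HIIT so defined trains participants above the heart rate at which the test would have stopped.

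**The case against.** **The 85% rule may belong to a separate screen.** The warm-up wording points to an earlier screening test, and the risk section elsewhere speaks of screening treadmill tests. But section IV.C describes one baseline graded test that both screens and yields VO2peak, the schedule has only a VO2peak row, and the endpoint rule refers to maximal exercise tests in the plural. The reading is possible but not established.

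**The exhaustion rules are not absolute.** Both allow the test to be stopped otherwise, and one refers to a section 4.1.2b that does not appear in the supplied text. The endpoints are also joined by 'or', so staff may in practice continue to fatigue. This is why the effect is conditional. It does not reconcile the rules.

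**Few may be affected.** The sample is sedentary and selected for fatigue, and many may tire first. The documents give no share. This stands.

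**Prescriptions are adjusted.** Intensity is progressed over weeks 3-8, staff may modify prescriptions from logs and observation, and heart rate is monitored continuously. This stands for the dose, although no passage says the maximal heart rate is re-estimated.

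A reader might infer more than the documents support:

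- That fitness gains will be spurious because a capped baseline is followed by an exhaustive week-16 test. No passage plans different stopping rules at the two visits.
- That every test stopped at 85% is materially submaximal, or that 19-38% bounds the error. The low end is near zero, and a true maximum above the predicted one could exceed the high end.
- That missing the 10-beat criterion rules out a recognised maximum. Two of three signs suffice, so a plateau plus the respiratory exchange ratio could still qualify.
- That HIIT would no longer be high intensity. Even the capped target is about 80-83% of predicted maximum, at the lower edge of the 80%-95% range in the Background.
- That heart rate reserve is wholly undefined. The term is spelled out; only its maximum is left open.

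**Conclusion.** The conflict between the stopping rules is real and should be resolved. That a stop at 85% fails the 10-beat criterion is firm arithmetic for any plausible predicted maximum. The understatement of VO2peak is not firm: it applies only to participants who reach 85% before tiring, in unknown number, and runs from near zero to roughly 20-40% in the illustration, which assumes equal true and predicted maxima and a resting rate of 55-85 bpm. The shift of about 19-23 bpm in the starting 90% target arises only if the capped peak is used for heart rate reserve, and it precedes any adjustment by staff.

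The effect is confined to exploratory outcome 2, the check that training was intense enough, and the starting prescription. The endpoint rule is the same in both arms. The primary 400-m walk is not measured by this test and its power calculation does not use VO2. Severity: minor.

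**What to change.** 1. Amend the endpoints bullet in section IV.D so that 85% of predicted maximal heart rate does not apply to the VO2peak test, or confine it to a named submaximal screen. Keep fatigue, unstable gait and all safety stops (a) to (i). This matches the exhaustion rule already in sections IV.C and IV.D.
2. State in the HIIT and CME descriptions in both sections that heart rate reserve uses the measured maximal heart rate from that test.
3. Record why each test ended, at baseline and week 16.
4. For participants already tested, keep one rule within each person. Where the baseline stop reason or peak heart rate shows a stop at 85%, use the same stop at week 16; where baseline ended in fatigue, run week 16 to exhaustion. Identify the capped group from baseline information only, since that test precedes randomisation, and review their heart-rate targets.
5. Report the week 0-16 VO2peak change with and without the capped group as a sensitivity analysis.

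The cost is one amendment with IRB and clinical review, one case-report field and one small sensitivity analysis. Clinical review is needed because removing a heart-rate endpoint in sedentary adults over 50 is a safety decision. The baseline stop reason may not have been kept for those already tested, in which case peak heart rate has to stand in for it. Table 1b plans UAB enrolment into the year starting April 2026, so later participants would benefit.
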